7.12 REPORTING PREGNANCY DURING THE CLINICAL TRIAL

Subjects in Phase 2 who are pregnant or expect to become pregnant prior to 3 months following the last dose will be excluded from participation in the clinical trial.

Subjects in Phase 3 who are pregnant or expect to become pregnant prior to the last dose will be excluded from participation in the clinical trial.

All pregnancies that occur from the time of first administration of clinical trial treatment through study completion (i.e., Day 393) will be reported to the Sponsor. If clinical trial site staff become aware that a subject becomes pregnant after the first dose in the clinical trial, she will not be given any additional treatments with the IP. A Pregnancy CRF Form will be completed by the site in EDC and submitted to the Sponsor within 24 hours after becoming aware of the pregnancy. In the event the EDC is unavailable, the Pregnancy and Pregnancy Outcome Report Form (paper) should be used and submitted to the Sponsor within 24 hours of becoming aware of the pregnancy.

The Investigator will report this event to their IRB/REB/EC in accordance with their policies and procedures.

The clinical trial site must request the subject's permission to query pregnancy outcome and follow the subject for outcome of the pregnancy. The subject will continue to be followed for safety assessments without receiving additional IP until clinical trial discharge in accordance with this protocol. Procedures that are contraindicated during pregnancy, including additional dose administrations, must not be performed. The Investigator should use clinical judgment regarding subsequent clinical trial-related blood collection based on the presence or absence of anemia in each subject.

Male subjects will be instructed through the ICF to immediately inform the Investigator if their partner becomes pregnant until study completion. A Pregnancy Form will be completed by the site and submitted to the Sponsor within 24 hours after becoming aware of the pregnancy. The pregnant partner will be asked to sign a Pregnancy Information Collection Consent Form to allow for follow-up on her pregnancy. If the authorization has been signed, the Investigator will collect and report details of the course and outcome of the pregnancy in the partner of a male subject exposed to IP. The site will update the

INO-4800	COVID19-311
Inovio Pharmaceuticals, Inc.	Clinical Protocol

Pregnancy Form with additional information on the course and outcome of the pregnancy and submit the form to the Sponsor.

If an Investigator is contacted by the male subject or his pregnant partner, the Investigator may provide information on the risks of the pregnancy and the possible effects on the fetus to support an informed decision in cooperation with the treating physician and/or obstetrician.

If the end of the pregnancy occurs after the clinical trial has been completed, the outcome will be reported directly to the Sponsor.

7.13 **REPORTING DEVICE-RELATED COMPLAINTS OR DEFICIENCIES**

All product complaints that meet the definition of device deficiency must be reported to the Sponsor within 10 days of discovery, with the exception of SAEs which require 24-hour reporting. The error reporting or complaint form must be completed and emailed to the Sponsor at [contact].

Device deficiencies include malfunctions, misuse or use errors and inadequate labeling. A malfunction is defined as the failure of a device to meet its performance specifications or otherwise perform as intended. The intended performance of a device refers to the intended use for which the device is labeled or marketed.

Any problems experienced during the treatment procedure including malfunctions of the device (e.g. significant device malfunction causing injury or resulting in a hazard which could cause injury to the subject or user), error messages displayed on the device screen following treatment, or errors that occur during the treatment procedure must immediately be reported to the Sponsor or its designee for evaluation. The Sponsor will review these reports for potential hazards that could cause an SAE. If Inovio determines that the malfunction could cause an SAE, the Inovio Medical Monitor will decide whether the Chair of the Safety Review Committee should be notified in accordance with Section 7.8.4.

7.14 NOTIFYING REGULATORY AUTHORITIES AND INSTITUTIONAL REVIEW BOARDS (IRBS)/RESEARCH ETHICS BOARDS (REBS)/ETHICS COMMITTEES (ECS) OF SAFETY INFORMATION

7.14.1 SPONSOR RESPONSIBILITIES

- Determine whether the safety information meets the requirements for expedited reporting to the applicable regulatory authorities;
- Prepare and submit the safety report to the applicable regulatory authorities;
- Send all participating PIs a safety report and Investigator Safety Letter (i.e., Dear Investigator Letter) that will include a statement if there is or is not any significant new safety information that might influence the risk-benefit assessment of the IP and/or study device, sufficient to consider changes in product administration or overall conduct of the clinical investigation.

7.14.2 PRINCIPAL INVESTIGATOR (PI) RESPONSIBILITIES

- Forward a copy of the safety report and Investigator Safety Letter (i.e., Dear Investigator Letter) to their IRB/REB/EC as soon as practical in accordance with the governing policy and/or procedures;
- Notify their IRB/REB/EC of safety information (i.e., SAEs, pregnancies, and AESIs) that occur at their clinical trial site in accordance with their local institutional policy.

INO-4800	COVID19-311
Inovio Pharmaceuticals, Inc.	Clinical Protocol

7.15 **POST-TRIAL REPORTING REQUIREMENTS**

PIs are not obligated to actively seek AEs or SAEs beyond the clinical trial reporting period. However, if the PI becomes aware of an AE or SAE that occurs after the Completion or Termination Visit and the event is deemed by the PI to be related to the clinical trial treatment, the PI should promptly document and report the event to the Sponsor.

7.16 CLINICAL TRIAL DISCONTINUATION

INOVIO reserves the right to discontinue the clinical trial at a site or at multiple sites for safety or administrative reasons at any time. In particular, a clinical trial site that does not recruit at a reasonable rate may be discontinued. Additionally, the clinical trial may be discontinued at any time by an IRB/REB/EC, INOVIO, or a regulatory authority as part of their duties to ensure that clinical trial subjects are protected.

If the clinical trial is discontinued and/or the clinical trial site closed for any reason, all IP and devices must be returned to INOVIO or its representative. The PI should ensure that their site file documents are complete prior to archiving, and provide copies of any requested documents to INOVIO for its Trial Master File (TMF).

8.0 STATISTICAL CONSIDERATIONS

8.1 STATISTICAL AND ANALYTICAL PLAN

The formal Statistical Analysis Plan is contained in the sections that follow.

8.2 **GENERAL CONSIDERATIONS**

The statistical analysis of the data will be performed by Inovio Pharmaceuticals or its representative.

This is an operationally seamless Phase 2/3 trial. The subjects and data from Phase 2 are independent from that of Phase 3.

Phase 2 Segment: This is a four-arm, multi-center, placebo-controlled, blinded, and randomized clinical trial in subjects at high risk of SARS-CoV-2 exposure. The trial's primary endpoints are antigen-specific cellular immune response measured by IFN-gamma ELISpot and neutralizing antibody responses. Secondary efficacy endpoints are safety measures. Exploratory endpoints are antigen-specific cellular immune response measured by flow cytometry and other T and B cell measures.

Phase 3 Segment: This is a two-arm, multi-center, placebo-controlled, double-blinded, and randomized clinical trial in subjects at high risk of SARS-CoV-2 exposure. The study's primary endpoint is the incidence of virologically-confirmed severe COVID-19 disease in subjects who are SARS-CoV-2 seronegative and RT-PCR negative at baseline starting 14 days after completion of the 2-dose regimen until 12 months post-dose 2. The primary hypothesis is that INO-4800 will be efficacious relative to placebo (relative efficacy > 30%). Secondary efficacy analyses involve non-severe cases, all cases, cases resulting in death, and cases among baseline SARS-CoV-2 seropositive subjects. Other secondary analyses concern safety and cellular and neutralizing antibody response. Exploratory analyses concern efficacy against variants, efficacy against asymptomatic infection, and binding antibody and cellular immunological measures.

INO-4800	COVID19-311
Inovio Pharmaceuticals, Inc.	Clinical Protocol

8.3 STATISTICAL HYPOTHESES

Phase 2 Segment: This is an estimation segment pertaining to immunogenicity and safety. There are no hypotheses.

Phase 3 Segment: The primary hypothesis of relative efficacy greater than 30% among baseline SARS-CoV-2 seronegative and RT-PCR negative subjects will be tested with H₀: $p \ge .70/(.70+k) vs. H_1: p < .70/(.70+k)$, where p is the true proportion of subjects with severe disease who receive INO-4800 relative to the total number of subjects with severe disease, and k is the total amount of follow-up time in the placebo group divided by the total amount of follow-up time in the INO-4800 group. There are no other formal hypotheses.

8.4 ANALYTICAL POPULATIONS

Analysis populations will be:

The per-protocol (PP) population includes all subjects who receive all doses of Study Treatments and have no protocol violations. Subjects in the PP population will be grouped to treatment arms as randomized. Subjects excluded from the PP population will be identified and documented prior to unblinding of the trial database. Analyses on the PP population among those who are baseline SARS-CoV-2 seronegative and RT-PCR negative will be primary for the analyses of efficacy in the Phase 3 segment of this trial.

The modified intention to treat (mITT) population includes all subjects who receive at least one dose of Study Treatment. Subjects in this population will be grouped to treatment arms as randomized. Analysis of the mITT population will be considered supportive for the corresponding PP population for the analyses of efficacy in the Phase 3 segment of this trial.

The intention to treat (ITT) population includes all subjects who are randomized. Subjects in this sample will be grouped to treatment arms as randomized. Analysis of the ITT population will be considered supportive for the corresponding PP population for the analyses of efficacy in the Phase 3 segment of this trial.

The safety analysis population includes all subjects who receive at least one dose of Study Treatment. Subjects will be analyzed according to the treatments received.

8.5 **DESCRIPTION OF STATISTICAL METHODS**

8.5.1 PRIMARY ANALYSIS

Phase 2 Segment

Post-baseline increases from baseline in interferon-γ ELISpot response magnitudes will be compared between treatment groups using differences in medians and associated non-parametric 95% CIs.

Post-baseline increases from baseline in neutralizing antibody response titers will be compared between treatment groups using ratios of geometric mean fold-rises and associated t-distribution based 95% CIs.

The summaries listed above will be stratified according to NP positive/negative status and according to prior receipt of any non-study prophylactic COVID-19 vaccine of the subjects. Valid samples for statistical analysis purposes will be those collected: at least 6 and no more than 30 days after Dose 2 for the Week 6 timepoint; at least 174 and no more than 198 days after Dose 2 for the Week 30 timepoint; and at least 356 and no more than 380

INO-4800	COVID19-311
Inovio Pharmaceuticals, Inc.	Clinical Protocol

days after Dose 2 for the Week 56 timepoint. Baseline is defined as the last measurement prior to the first treatment administration.

The PP population will be used for these immunogenicity analyses.

Phase 3 Segment

Among subjects who are SARS-CoV-2 seronegative and RT-PCR negative at baseline, the primary hypothesis of relative efficacy greater than 30% will be tested with H₀: $p \ge 0.70/(0.70+k) vs$. H₁: p < 0.70/(0.70+k), where p is the true proportion of subjects with severe disease who receive INO-4800 relative to the total number of subjects with severe disease, and k is the total amount of follow-up time in the placebo group divided by the total amount of follow-up time in the INO-4800 group.

A p-value for this hypothesis test and corresponding confidence interval will be computed based on the exact binomial method of Clopper-Pearson. Success will be concluded if the one-sided p-value is <0.025 and the corresponding lower bound of the two-sided 95% Cl for efficacy exceeds 30%.

For calculating k, an individual subject's follow-up time is either:

- the date of first disease diagnosis date of the start of surveillance period +1 (for subjects who are cases), or
- the date of last follow-up date of the start of surveillance period +1 (for subjects who are non-cases).

This methodology is based on the following. Assuming that the number of subjects who are cases in the INO-4800 group follows a Poisson distribution with parameter λ_v and the number of subjects who are cases in the placebo group follows a Poisson distribution with parameter λ_c , then conditional on total number of subjects with cases, t, the number of subjects who are cases in the INO-4800 group follows a binomial distribution with parameters (t, $p = \lambda_v/(\lambda_v + \lambda_c)$). The relationship between p and efficacy is: efficacy = (1-(1+k)p)/(1-p). Therefore, testing efficacy > 30% corresponds to testing p < 0.70/(0.70+k). Similarly, the confidence interval for efficacy is (1-(1+k)UB_p)/(1-UB_p), (1-(1+k)LB_p)/(1-LB_p), where UB and LB are the Clopper-Pearson upper and lower limits for the proportion.

The efficacy time frame is defined by symptoms beginning at any time starting from 14 days after Dose 2 and ending 12 months after Dose 2. Subjects identified as cases that started prior to this time point will be excluded. Subjects with multiple instances meeting the case definition will be counted only once, using the first such instance.

The PP population will be primary for the analysis of efficacy in this trial. Efficacy analysis using the mITT population will also be conducted counting cases from 14 days postdose 1 as a supportive analysis. The ITT population will also be used for a supportive analysis counting cases starting from randomization.

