This segment of the trial is case-driven. Among subjects who are seronegative and RT-PCR negative at baseline, a total of 17 observed severe cases will be required for 90% power to declare the vaccine efficacious (>30%), assuming a true efficacy of 90%. A sample size of 10,002 seronegative subjects is expected to be required to achieve the 17 severe cases assuming an underlying attack rate of 0.4%. The actual sample size may differ if the observed attack rate is different than projected. If the criteria for efficacy are met, placebo-recipients will be offered the active product.

The primary efficacy endpoint window will begin 14 days post-dose 2 and will end at 12 months post-dose 2. All Phase 3 segment subjects will be followed for 56 weeks from the Day 0 dosing [i.e., Week 56 will be the planned End of Study (EOS) visit for this segment of the trial].

External Committee Reviews

INO-4800	COVID19-311
Inovio Pharmaceuticals, Inc.	Clinical Protocol

For both the Phase 2 and 3 segments, the Data Safety Monitoring Board (DSMB) will convene regularly to review all available unblinded safety data, and additionally upon completion of the Week 8 phone call visit for all subjects enrolled during the Phase 2 segment. For the Phase 3 segment, the DSMB will also review efficacy in an unblinded fashion. Additionally, for Phase 3, an independent, blinded Endpoint Adjudication Committee (EAC) will review and confirm COVID-19 cases.

Details of each committee's scope will be provided in the respective charters.

3.1 **PRIMARY OBJECTIVES**

See Table 6.

3.2 **PRIMARY ENDPOINTS**

Table 6: Primary Objectives and Associated Endpoints

Phase 2 Primary Objective	Phase 2 Primary Endpoints
 Evaluate the cellular and humoral immune response to INO-4800 	1a. Antigen-specific cellular immune response measured by IFN-gamma ELISpot assay
administered by ID injection followed immediately by EP	1b. Neutralizing antibody response measured by a pseudovirus-based neutralization assay
Phase 3 Primary Objective	Phase 3 Associated Primary Endpoint
 Evaluate the efficacy of INO-4800 in the prevention of severe COVID-19 disease in subjects who are SARS- CoV-2 seronegative and RT-PCR negative at baseline 	 Incidence of virologically-confirmed severe COVID-19 disease starting 14 days after completion of the 2-dose regimen until 12 months post-dose 2 (End of Study (EOS)) in subjects who are SARS-CoV-2 seronegative and RT-PCR negative at baseline

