Unless a subject refuses to continue participation, all follow-up visits and procedures should be completed as indicated in the Schedule of Events (Table 3 and Table 4) following the second dose whether or not the subject has completed both doses.

If a subject receives a non-study COVID-19 vaccine either authorized under emergency use or licensed, during the trial, the subject should provide details of the vaccine to study staff and the Investigator should enter the details as a concomitant medication. The subject should be advised that there is inadequate information regarding the safety and effectiveness of other COVID-19 vaccines when received following the receipt of INO-4800. Furthermore, the subject should be requested to remain in the trial (according to the Schedule of Events outlined in Tables 3 and 4).

Should a subject fail to attend the clinic for a required study visit, the site should attempt to contact the subject and reschedule the missed visit as soon as possible. In cases where

INO-4800	COVID19-311
Inovio Pharmaceuticals, Inc.	Clinical Protocol

the subject does not return for the rescheduled visit or cannot be reached to reschedule the missed visit, the site should make every effort to regain contact with the subject (3 telephone calls and if that fails, then a certified letter to the subject's last known mailing address) so that the subject's disposition can be considered as withdrawn from the study (i.e. lost to follow-up). If the contact with subject is re-established, site should contact medical monitor to discuss whether subject can continue study treatment or follow-up visits for the study. For all other subjects withdrawing from the study, an alternative reason for discontinuation should be recorded in the eCRF.

Reasons for discontinuation/withdrawal from the trial may include but are not limited to the following:

- Subject withdrawal of consent at any time;
- Any medical condition that the Investigator or Sponsor determines may jeopardize the subject's safety if he or she continues in the trial;
- Investigator, DSMB or Sponsor determines it is in the best interest of the subject;
- Subject non-compliance.

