Actual or estimated start and stop dates must be provided. This information will be obtained from the subject and/or any available medical records. The indication for the medication, dose, and dose regimen will be documented.

Therapy considered necessary for the subject's welfare may be given at the discretion of the Investigator or medical provider. If the permissibility of a specific medication/treatment is in question, please contact the Medical Monitor.

The decision to administer a prohibited medication/treatment (Section 6.4.7) is made with the safety of the clinical trial subject as the primary consideration. When possible, the Sponsor should be notified before the prohibited medication/treatment is administered.

6.4.7 **RESTRICTIONS**

In the Phase 2 segment of the trial, subjects should refrain from becoming pregnant until 3 months following the last dose of investigational product by using appropriate

INO-4800	COVID19-311
Inovio Pharmaceuticals, Inc.	Clinical Protocol

contraceptive measures (see Section 4.1.1). In the Phase 3 segment of the trial, subjects should refrain from becoming pregnant until receipt of the last dose of investigation product by using appropriate contraceptive measures (See Section 4.1).

Subjects must not receive any non-study related vaccine (e.g., influenza vaccine) within 2 weeks prior to the first dose of IP, or within 2 weeks of (before or after) any subsequent dose of IP.

Subjects must not have fever (oral temperature \geq 38.0 degrees Celsius or 100.4° Fahrenheit) within 72 hours prior to each dosing.

Subjects should not receive hydroxychloroquine during the trial. In the Phase 3 segment, subjects should not receive any other drug/vaccine intended as COVID-19 prophylaxis during the trial.

For subjects in the Phase 2 segment of the trial, the receipt of any non-study prophylactic COVID-19 vaccine (authorized under emergency use or licensed) is no longer restricted, based upon increasing availability of EUA vaccine and completion of the Phase 2 data for purposes of Phase 3 dose selection.

If a subject informs the site of their intent to receive a non-study prophylactic COVID-19 vaccine (available either under emergency use or when licensed), the subject should be informed that the safety and effectiveness of receiving INO-4800 followed by receipt of another COVID-19 vaccine has not been studied.

Subjects should not participate in any other interventional trials for the duration of this trial.

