8.5.9.3 Concomitant Medications

Concomitant medications are those used during the course of the trial (on or after Day 0). Partial stop dates of concomitant medications will be assumed to be the latest possible date consistent with the partial date; start dates will not be imputed. Data for all concomitant medications will be summarized with percentages by treatment arm, for the ITT and PP populations. These summaries will be performed according to Phase. For the Phase 3 segment, the analyses listed above will also be performed according to SARS-CoV-2 serostatus at baseline.

8.6 **SAMPLE SIZE/POWER**

Phase 3 segment: The trial is case-driven. A total of 17 observed severe cases among baseline SARS-CoV-2 seronegative and RT-PCR negative subjects will be required to provide 90% power to declare the vaccine efficacious (>30%), assuming a true efficacy of 90% and utilizing the methodology described in Section 8.5.1. A sample size of 10,002 baseline SARS-CoV-2 seronegative subjects is expected to be required to achieve this number of cases assuming an underlying attack rate of approximately 0.4%.

8.7 **RANDOMIZATION AND BLINDING**

Phase 2 Segment

Subjects will be randomized (3 INO-4800 1.0 mg, one injection: 3 INO-4800 2.0 mg, two injections:1 Placebo, one injection: 1 Placebo, two injections).

The study is blinded. It is double-blinded within dose group. Randomization and blinding will avoid bias in the assignment of subjects to treatment, increase the likelihood that known and unknown subject attributes (e.g., demographics and other baseline characteristics) are evenly balanced between treatment groups, and enable valid statistical comparisons between treatment groups. Subject treatment assignments will be unblinded after Phase 2 subjects have reached the Week 30 visit.

Phase 3 Segment

Subjects will be randomized (2 INO-4800:1 Placebo). Randomization will be stratified according to two factors, each with two levels: a) age-group age category (18-50 years vs. ≥51 years) on Day 0, and b) presence or absence on Day 0 of underlying medical conditions that increase risk of severe COVID-19 disease, per US CDC criteria.

The study is double-blinded. Randomization and blinding will avoid bias in the assignment of subjects to treatment, increase the likelihood that known and unknown subject attributes

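### The Phase 3 primary analysis has no sound rule for a non-study COVID-19 vaccine taken during follow-up: read literally, the per-protocol set drops the subject and any earlier severe case; read otherwise, post-vaccine time counts for the randomised arm.

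*Protocol*

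**What the plan says.** All references are to protocol version 7.0.

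- **Follow-up time (Section 8.5.1).** The ratio k is placebo follow-up time over INO-4800 follow-up time. A case contributes time to first diagnosis. A non-case contributes the date of last follow-up minus the "date of the start of surveillance period +1 (for subjects who are non-cases"). No other end date is given.
- **Outside vaccination (Sections 4.3, 6.4.6 and 6.4.7).** The restriction reads: "In the Phase 3 segment, subjects should not receive any other drug/vaccine intended as COVID-19 prophylaxis during the trial". A subject who nevertheless takes a non-study vaccine has it recorded as a concomitant medication, with dates. Section 4.3 adds: "Furthermore, the subject should be requested to remain in the trial".
- **Populations (Section 8.4).** The per-protocol (PP) set, which is primary for efficacy, takes subjects who received all doses and have no protocol violations. The term is not defined and has no time limit. mITT and ITT keep everyone as randomised and are supportive.
- **Contrast with Phase 2.** The Phase 2 immunogenicity and safety summaries are split by receipt of a non-study vaccine (Sections 8.5.1, 8.5.3 and 8.5.9.2). The Phase 3 efficacy analysis has no counterpart.
- **Test and size (Sections 8.5.1 and 8.6).** "Success will be concluded if the one-sided p-value is <0.025", with a matching condition on the lower 95% confidence limit. On size, Section 8.6 states: "A total of 17 observed severe cases among baseline SARS-CoV-2 seronegative and RT-PCR negative subjects will be required". The target behind that number is 90% power against the 30% margin when true efficacy is 90%.

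**The concern.** The efficacy window runs to 12 months after dose 2, and Section 1.4.3 notes that emergency-use vaccines are becoming available in many countries. Some outside vaccination during the window is therefore foreseeable, and version 7.0 already provides for it in data collection and in Phase 2.

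The Phase 3 primary analysis can be run in two ways, neither of them satisfactory. If receipt breaches Section 6.4.7 and so counts as a violation, the subject leaves the PP set because of something that happened after the outcome window opened. A severe case in month 3 would be lost because of a vaccine in month 8. That discards valid events from a small trial, and it is a selection effect if the decision to be vaccinated is related to risk or to suspected assignment. If receipt is not a violation, time and cases under another vaccine's protection are credited to INO-4800 or placebo, which pulls the estimate towards the null when uptake is equal.

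This is not simply detail held for a later document. Section 8.1 says the formal statistical analysis plan is contained in the protocol, and Section 8.5.1 fixes the end dates.

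**Working it through.** **Inputs from the protocol.** One-sided alpha 0.025; 2:1 randomisation, so planned k = 0.5; true efficacy 90%; 17 severe cases; N = 10,002; attack rate about 0.4% (Sections 8.5.1, 8.6 and 8.7). On the null, Section 8.5.1 states that "testing efficacy > 30% corresponds to testing p < 0.70/(0.70+k").

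**Reproducing the plan's own figure.**
- Null proportion: 0.70/(0.70 + 0.5) = 0.5833. Alternative: 0.10/(0.10 + 0.5) = 0.1667.
- With 17 cases the largest rejecting count in the INO-4800 arm is 5: P(X ≤ 5 | 0.5833) = 0.0153, and power P(X ≤ 5 | 0.1667) = 95.0%.
- Power moves in a saw-tooth: 93.1% at 14 cases, 91.0% at 15, 88.7% at 16, 95.0% at 17, 93.5% at 18. So 17 is the smallest count from which power stays at or above 90%, and the stated figure reproduces.
- Reading the attack rate as the placebo risk, expected cases are 10,002 × 0.004 × (1/3 + 0.1 × 2/3) = 16.0. At 0.425% they are 17.0, so N reproduces within rounding.

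**Assumptions added here.** The protocol gives no uptake of non-study vaccine. I take f = 20% and 30%, equal in both arms, unrelated to risk and spread evenly over follow-up, so a fraction f/2 of person-time falls after the vaccine. N is fixed at 10,002. Power is the exact binomial power averaged over a Poisson number of cases.

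**PP analysis: deletion against censoring.** Expected cases are 16.0 × (1 − f) with deletion and 16.0 × (1 − f/2) with censoring.

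| Uptake | Deletion: cases, power | Censoring: cases, power | Cases lost by deletion beyond censoring |
|---|---|---|---|
| 0% | 16.0, 89.6% | 16.0, 89.6% | 0 |
| 20% | 12.8, 80.9% | 14.4, 85.9% | 1.6 |
| 30% | 11.2, 74.3% | 13.6, 83.6% | 2.4 |

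The loss due to deleting rather than censoring is 85.9 − 80.9 = 5.0 points at 20% uptake and 83.6 − 74.3 = 9.3 points at 30%.

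**The other reading: uncensored time.** Let g be the post-vaccine share of person-time, and assume the outside vaccine cuts severe disease by 90% and sets the risk in both arms after receipt. Estimated efficacy = 1 − [(1 − g)(1 − VE) + 0.1g] / [(1 − g) + 0.1g]. At 30% uptake, g = 0.15:
- VE 90%: 1 − 0.100/0.865 = 88.4%.
- VE 60%: 1 − 0.355/0.865 = 59.0%.

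With unequal uptake at mid-window (assumed 20% in the INO-4800 arm, 40% in placebo), the post-vaccine shares are 0.10 and 0.20:
- VE 90%: 1 − 0.10/0.82 = 87.8%.
- VE 60%: 1 − 0.37/0.82 = 54.9%.
- k is 0.500 uncensored, 0.444 with censoring and 0.375 with deletion.

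**The case against.** **Deletion is inferred.** No sentence says that a vaccine taken after dosing excludes a subject from PP. Section 4.3 provides a managed pathway, Section 6.4.7 says only that subjects should not receive other prophylaxis, and Section 8.4 settles exclusions before unblinding. This stands: a reader might infer that the protocol expressly deletes these subjects, and it does not. But no rule governs the decision, and the alternative reading leaves uncensored time in the primary analysis.

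**The trial is case-driven.** Section 3.0 allows the sample size to change with the attack rate. If 17 evaluable cases accrue, power is 95.0%. This stands: the power figures above hold only at fixed N, and otherwise the cost is time. It does not remove the selection effect.

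**Uptake may be low.** Planned receipt of another vaccine is an exclusion criterion (Section 4.2.2) and receipt is restricted. The 20% and 30% are assumptions.

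**Uncensored mITT and ITT.** A reader might call these wrong. They are a defensible treatment-policy choice and they retain every pre-vaccine case.

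**Crossover.** A reader might add that placebo recipients given INO-4800 contaminate the primary result. Section 3.0 says: "If the criteria for efficacy are met, placebo-recipients will be offered the active product". That follows a met criterion, and version 7.0 has no efficacy interim analysis, so the primary test is not affected.

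**Censoring has its own weakness.** It is informative if uptake depends on suspected assignment. This stands, although double-blinding and the rule in Section 5.2.1 against unblinding for outside-vaccine decisions reduce the risk.

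**Conclusion.** The point holds for the primary PP analysis. Sections 8.4 and 8.5.1 leave either whole-subject deletion, with earlier severe cases, or uncensored post-vaccine time. Censoring at receipt is better than both.

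At fixed N, and with the assumed 20% to 30% uptake, deletion costs about 5 to 9 points of power beyond what censoring costs. The full fall from 89.6% should not be attributed to the deletion rule, because part of it remains under censoring.

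Dilution under the other reading is modest and towards the null with equal uptake: about 1.6 points at a true efficacy of 90% and 1.0 point at 60%, for 30% uptake spread evenly. A reader might infer a larger drop, to 86% and 57%, by taking 30% of person-time as post-vaccine. With even spread that would need 60% uptake. Unequal uptake makes the shift larger.

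The 17-case figure and N are not in dispute. This is a should-fix.

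**What to change.** Amend Sections 8.4 and 8.5.1 before unblinding:

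1. For the primary PP analysis, state that receipt of a non-study COVID-19 vaccine after the start of surveillance is not a reason for exclusion. Time and cases before receipt are kept.
2. In that analysis, end both the follow-up time for k and case counting at the earliest of case onset, receipt of a non-study COVID-19 vaccine, last follow-up, or 12 months after dose 2.
3. Tabulate receipt and its timing by arm, so that unequal uptake can be seen.
4. Keep mITT and ITT uncensored and label them as treatment-policy analyses. A censored version of either is optional.

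The cost is a few sentences and one derived date. Vaccine details and dates are already collected under Sections 4.3 and 6.4.6, and no study procedure changes. The downsides are that some post-vaccine person-time goes unused in the primary analysis, and that censoring can be informative if uptake follows suspected assignment. The by-arm table and the uncensored mITT and ITT results help to judge the second.
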